7.1.5 Month 4/ End of HALT-AD Program

Following completion of the 3-Month HALT-AD program, participants will complete the following assessments remotely via the REDcap survey tool (total estimated time approximately 1.0 hour):

- HALT-AD User Experience Survey
- Net Promoter Score Survey
- HALT-AD Course Acceptability Survey
- Facilitated Discussion Group Acceptability Survey
- Knowledge Assessment Survey

Participants will also complete the following end of study assessments directly within the online HALT-AD program (total estimated time approximately 30 min-1.0 hour):

- New General Self-Efficacy Scale (NGSE)
- Lifestyle Risk Assessment
- Review of Goals

7.1.6 Post-Pilot Focus Groups

Following completion of the 3-month HALT-AD program, participants may be invited to participate in an end of study remote focus group(s) to further evaluate user-experience and satisfaction with HALT-AD. This will allow the study team to address in more detail the components that have been surveyed in the questionnaires on usability and acceptability: (e.g. level of difficulty and interest in the content, strengths and weaknesses, confidence in the content, applicability and impact in everyday life, clarifications, quality of design, animation and visual effects, effort needed, motivation for behavioral change). Participant feedback and responses will be used to make any necessary changes to the web-based HALT-AD program prior to launch of the full program. Total time to participate in the focus group is approximately 2 hours (1 hour to discuss web-based platform and 1 hour to discuss facilitated discussion groups).

Focus groups will be conducted remotely over video-call in smaller groups of approximately 5-10 other participants. Participants will need access to a computer, tablet or mobile device capable of making video-calls. The focus group discussions will be audio-recorded for transcription. All identifiable information will be removed from the transcripts and replaced by unique coded Participant ID number. Recordings will be destroyed once the focus group discussion has been transcribed.

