4.3 Exploratory Outcomes

- 4.3.1 Users' acceptability of the HALT-AD program content will be determined by:
 - HALT-AD Course Acceptability Survey
 - Focus group discussion
- 4.3.2 Users' acceptability and satisfaction with the facilitated support discussion groups will be determined by:
 - Facilitated Discussion Group Acceptability Survey
 - Focus group discussion
- 4.3.3 The usability of the online platform will be evaluated by:
 - HALT-AD User Experience Survey
 - Net Promotor Score Survey

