16.1.2 HALT-AD Course Acceptability Survey

- 1) Overall, was it **easy** to understand the information presented in the courses?
 - Not at all easy
 - Slightly easy
 - Moderately easy
 - Very easy (*skip to question 3*)
 - Extremely easy (*skip to question 3*)

- 2) What changes can we make for information to become more understandable?

- 3) Rate the overall **amount of information** presented in the courses:
 - Too little
 - About right
 - Too much

- 4) Generally, was the information presented in the courses **boring**?

- Not at all boring (skip to question 6)
- Slightly boring
- Moderately boring
- Very boring
- Extremely boring

5) What changes can we make for information to become less boring?

6) Generally, was the information presented to you in the courses **helpful**?

- Not at all helpful
- Slightly helpful
- Moderately helpful
- Very helpful
- Extremely helpful

7) Generally, did you find the **activities** in the courses to be **interesting**?

- Not at all interesting
- Slightly interesting
- Moderately interesting
- Very interesting (*skip to question 9*)
- Extremely interesting (*skip to question 9*)

8) How can we change the activities to make them more interesting?

9) Generally, did you find the **activities** in the courses to be **helpful**?

- Not at all helpful (*skip to question 11*)
- Slightly helpful (*skip to question 11*)
- Moderately helpful (*skip to question 11*)
- Very helpful
- Extremely helpful

10) In what ways were the activities helpful? (*skip to question 12*)

11) How can we change the activities to make them more helpful?

12) Generally, were the **quiz questions clear**?

- Not at all clear
- Slightly clear
- Moderately clear
- Very clear
- Extremely clear

13) Overall, was the information in the courses **new** to you?

- Not at all new
- Slightly new
- Moderately new
- Very new
- Extremely new

14) Overall, did you find the information in the courses to be **uplifting**?

- not at all uplifting
- Slightly uplifting
- Moderately uplifting
- Very uplifting
- extremely uplifting

15) How likely are you to recommend these courses to a family member, friend or colleague?

- extremely unlikely
- Unlikely
- Likely
- Extremely likely

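### Participants who withdraw give no acceptability data: surveys and focus groups both come after the 3-month program, and nothing is collected at early discontinuation

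*Combined protocol and SAP*

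**What the plan says.** Sections 4.3.1 and 4.3.2 give each acceptability aim two sources.

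- **Aim 3 (course content).** Users' "acceptability of the HALT-AD program content will be determined by" the Course Acceptability Survey and focus group discussion.
- **Aim 4 (discussion groups).** Users' "acceptability and satisfaction with the facilitated support discussion groups will be determined by" a dedicated survey and focus group discussion.

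The surveys fall at Month 4. Section 7.1.5 reads: "Following completion of the 3-Month HALT-AD program, participants will complete the following assessments remotely via the REDcap survey tool". Section 7.1.6 places the focus groups after the program too, but in weaker terms: "Following completion of the 3-month HALT-AD program, participants may be invited to participate in an end of study remote focus group(s"). It gives no selection rule. It describes the groups as a way to "address in more detail the components that have been surveyed in the questionnaires on usability and acceptability", and adds: "Participant feedback and responses will be used to make any necessary changes to the web-based HALT-AD program".

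Section 10.0 allows withdrawal at any time and lists grounds for discontinuation. It provides no exit survey, exit interview or focus group invitation. Section 12.1 has no rule for missing acceptability data. Section 4.1 makes the percentage of participants completing all courses a primary outcome, so the plan itself allows for non-completion.

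**The concern.** The pilot exists to improve a prototype, and those who leave may know best what made them leave. The plan will count people who do not finish, but it has no step that ensures their views are heard. If early leavers are less favourable than those who stay, a survey summary based on respondents alone will overstate acceptability, and the focus group themes will lack the reasons for leaving. Section 12.1 treats the qualitative analysis as complete once no new themes appear. Saturation among people who stayed says nothing about themes held only by those who left.

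**Working it through.** The plan states no acceptability figure and no dropout rate, so there is no figure of its own to reproduce. The check has three parts.

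**1. Who is reached, by source**

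| Participant | Month 4 surveys (7.1.5) | Focus groups (7.1.6) | Section 10.0 |
|---|---|---|---|
| Stays, likes the program | Yes | If invited | – |
| Stays, dislikes the program | Yes | If invited | – |
| Stops the courses, does not withdraw | Yes, if completion means end of period | Same condition, and if invited | – |
| Withdraws | No provision | No provision | Nothing collected |

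Only the last row is missed on any reading. The third row depends on a word that the plan does not define.

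**2. Effect on a survey-based proportion**

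Input from the plan: N = 20 enrolled (section 6.0). Assumed: d participants withdraw, and x of the remaining N − d are favourable. The observed value is x/(N − d). The value among all enrolled lies between x/N (no leaver favourable) and (x + d)/N (every leaver favourable).

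| d (assumed) | x (assumed) | Observed | Lower bound | Upper bound |
|---|---|---|---|---|
| 0 | 18 | 18/20 = 90% | 18/20 = 90% | 18/20 = 90% |
| 2 | 16 | 16/18 = 88.9% | 16/20 = 80% | 18/20 = 90% |
| 4 | 14 | 14/16 = 87.5% | 14/20 = 70% | 18/20 = 90% |
| 6 | 13 | 13/14 = 92.9% | 13/20 = 65% | 19/20 = 95% |

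With d = 4, having 0, 1, 2, 3 or 4 favourable leavers gives 70%, 75%, 80%, 85% or 90%. The observed 87.5% is too high unless all four leavers are favourable. With no withdrawals and all surveys returned, there is no gap.

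**3. Effect of discretionary invitation on the focus groups**

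Assume m = 4 dissatisfied participants among the 20 and k taking part, chosen at random. The chance that none of the four is included is C(16, k)/C(20, k).

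- k = 5: 4,368/15,504 = 28.2%
- k = 10: 8,008/184,756 = 4.3%
- k = 20: 0%

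Random choice is itself an assumption, since the plan gives no rule. On capacity, section 7.1.6 says: "Focus groups will be conducted remotely over video-call in smaller groups of approximately 5-10 other participants". At 10 per group, 20/10 = 2 sessions hold everyone; at 5 per group, 20/5 = 4.

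**The case against.** A reader might infer that the acceptability evidence for both aims leaves out everyone who disliked the program. The documents do not support that, for these reasons.

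- **The surveys are not discretionary.** Section 7.1.5 has participants complete them, and the Course Acceptability Survey in Appendix 2 has negative options and open items such as "What changes can we make for information to become less boring". Someone who disliked the courses but stayed can say so. For Aim 4 this is less certain in detail, because section 9.2.7 leaves the discussion group survey still to be written.
- **Nothing excludes dissatisfied participants from the focus groups.** An open invitation rule creates a risk of selection; it does not state an exclusion.
- **Completion most naturally marks a time point.** Section 7.1.5 is headed Month 4, section 7.2.3.2 refers to the end of the program, and the Schedule of Events places focus groups at Month 4 with no course-completion condition. Finishing the courses is a separate measure in sections 4.1 and 7.4. On this reading, someone who stopped the courses without withdrawing remains eligible.

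A reader might also set 2/16 = 12.5% not favourable among those who stay against (2 + 4)/20 = 30% among all enrolled. That is the worst end of the four-withdrawal scenario above, and it describes a proportion that focus groups, which yield themes, do not produce.

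Focus groups are also not the only input to the redesign: section 1.2 lists program data, usability and citizen advisors as well. Inviting a subset can be a legitimate qualitative choice.

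All of this stands. It narrows the gap to people who withdraw, plus an undefined word and an unstated invitation rule. It does not close that gap, because the surveys come as late as the focus groups.

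**Conclusion.** The point holds in a limited form. As written, people who withdraw contribute no acceptability data from either source, and their reasons for stopping are not collected. Who is invited to the focus groups is left open.

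The size cannot be determined from the plan. Under the assumed four withdrawals with 14 of 16 favourable, the figure for all enrolled could be anywhere from 70% to 90%, against an observed 87.5%. With no withdrawals and full survey return, the effect is nil. An upward bias also requires that leavers be less favourable than stayers, which is plausible but not shown.

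Severity is minor: acceptability is an exploratory outcome (section 4.3) in a 20-person pilot that was not powered (section 12.2). The point is still worth acting on, because feedback for the second prototype is a stated purpose of the study and the remedy is cheap.

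**What to change.** 1. **Section 7.1.6:** state that all enrolled participants will be invited to a focus group, including those who did not finish the courses or stopped early, unless they withdrew consent to contact. Define completion as the end of the 3-month period.
2. **Section 10.0:** offer the existing acceptability surveys at early discontinuation.
3. **Section 12.1:** report focus group invitation, focus group attendance and survey response against all enrolled, and give completion status alongside the survey results and themes.

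The cost is a few sentences, a few more invitations and possibly one more group session. No new survey beyond those already planned is needed, and section 7.5 already leaves compensation unchanged by withdrawal after Baseline. Early leavers may decline, in which case the reported response counts would at least show the gap.

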7.2 HALT-AD PROGRAM DESCRIPTION

7.2.1 Overview

HALT-AD is a novel bilingual program that will focus on preventing dementia. The program will include an easily accessed interactive, online web-based program that will direct participants to engage in different evidence-based content, to learn and become motivated to change their personalized profile of modifiable risk factors. It will include up to date information and evidence for lifestyle risk factor modification that can be addressed to promote brain health and reduce dementia risk. HALT-AD will include learning courses that will be aligned with those modifiable risk factors with significant population attributable risk of dementia.

[figure not shown]
HALT-AD is a bilingual bicultural program with options to participate in English or Spanish. The program is developed as a collaborative effort by UCSD investigators with recognized expertise in the program's content areas, along with significant input from older-adult Citizen Advisors and Promotores (community health workers), ensuring cultural relevance and assisting in feedback within its iterative development.

For this initial pilot study, HALT-AD will focus on up to four initial learning courses:

- Introductory Course
- Diet
- Sleep or Physical Activity
- Social Connectivity and Loneliness

Once the full program is developed, additional learning courses will include, vascular factors (hypertension, diabetes, obesity and cerebrovascular health), physical activity (exercise), mood (depression and stress), mindfulness, sensory (vision and hearing) and cognitive training. Topic matters will also include advice on how to navigate the healthcare system as well as courses myths and popular misconceptions regarding brain health, and how risk profiles may differ in men and women.

Figure 1. HALT-AD Program Description

7.2.2 Program Registration

Participants will receive instructions on how to register and participate in the program at the baseline study visit. As outlined in Figure 1 at enrollment, participants will join a welcome page that will explain the program, followed by registration and creation of a personal password. Their registration will include demographic and lifestyle questions.

7.2.3 Program Elements

Participants will be provided access to HALT-AD where they will participate for approximately 1-2 hours a month for 3 months, from home, with their own devices and at their own time. Information within the courses will contain scientific evidence, explanation of principles and mechanisms that underlie positive effects, specific recommendations (e.g. a healthy recipe to make at home), suggestions to improve behavior in everyday life and typical barriers and tips to circumvent them. Participants will also be able to revisit course material as often as they would like. Additional program elements will also include interactive activities, quizzes and a resource library.

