4.2 Secondary Outcomes

- 4.2.1 Preliminary evidence on the effectiveness of the program in changing knowledge, self-efficacy, and dementia-related lifestyle risk factors will be evaluated by:
 - Change from baseline in knowledge on the HALT-AD knowledge assessment survey at 4 months
 - Change from baseline in self-efficacy on the New General Self-Efficacy Scale (NGSE) at 4 months
 - Change from baseline in lifestyle risk on the HALT-AD Lifestyle Risk Assessment Survey at 4 months

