7.1.4 Baseline/ HALT-AD Program Launch (+/- 30 days)

Participants who are confirmed to be eligible to participate and enrolled in the study, will then complete the following baseline assessments. These may be completed on the same day as the screening visit, as long as they are conducted following the screening assessments and confirmation of eligibility (total estimated time approximately 30 min):

- Documentation of demographics, medical history (including past medical procedures and family history), medications
- Self-Report Height, Weight
- Body Mass Index (BMI) calculation (based on self-report current height and weight)
- Knowledge Assessment Survey

Following completion of the above baseline assessments, participants will be enrolled in the HALT-AD online program and will be provided with instructions for logging into and beginning their participation in the program (see section 7.2 for a complete description of HALT-AD).

Participants will also complete the following baseline assessments directly within the online HALT-AD program (total estimated time approximately 30 min-1.0 hour):

- New General Self-Efficacy Scale (NGSE)
- Lifestyle Risk Assessment
- Goal setting

Throughout the participants' participation in the 3-Month HALT-AD program, a study coordinator will maintain contact with the participant by telephone or email to check-in with participants, provide reminders about upcoming HALT-AD program elements and be available to answer any questions that may arise. E-mails will be sent from a secure UCSD health e-mail account.

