16.1 APPENDIX 2: Survey Instruments

16.1.1 Knowledge Assessment Survey

Below are some statements about brain health and dementia prevention. Please read each statement carefully and choose whether you think the statement is True or False.

1. If I am healthy, my brain should not age at all over time.
2. As I age, I will most certainly have dementia.
3. People from Hispanic or African American backgrounds have a higher risk of developing Alzheimer's Disease.
4. Being physically inactive and being obese are two examples of factors that can increase our chances of developing Alzheimer's Disease.
5. Hanna may avoid dementia by making healthier lifestyle changes such as getting better sleep, eating a healthier diet, and being more physically active.
6. There are many reasons why older adults may feel lonely. Reasons include losing family members, facing difficulties in moving around, and well as feeling empty and sad.
7. Everyone experiences loneliness the same way. It is not personal, and it does not differ across people.
8. People that are lonely have an increase in abnormal proteins in their brain. The accumulation of abnormal proteins in the brain occurs during the development of Alzheimer's Disease.
9. If you are feeling lonely, there is nothing you can do to overcome your loneliness.
10. Sometimes, when we are very lonely, making personal initiatives such as joining a volunteering social group does not always work. That's totally OK.
11. An average adult should be getting 7-9 hours of sleep a day. Getting 4-6 hours of sleep a night on a weekly basis does not significantly affect brain function, since it is only a few hours less than the recommended amount.
12. When we haven't sleep for 24 hours, our cognitive abilities decrease to a point that is like when someone is legally drunk.
13. Lack of sleep can affect our health in a variety of ways, including increasing our risk of developing a stroke, weakening our immune defenses, and contributing weight gain.
14. Developing new habits and routines like going outdoors, practicing mindfulness, cultivating social relationships, creating a daily routine, reducing caffeine intake at night, and seeking help when needed are all lifestyle changes that can improve sleep.
15. Because sleep issues are so personal, there are no treatments.

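### At Month 4 the course content is an extra source of answers to the knowledge survey that did not exist at baseline, and the survey never asks for unaided answers

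*Combined protocol and SAP*

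**What the plan says.** Section 4.2 lists as a secondary outcome "Change from baseline in knowledge on the HALT-AD knowledge assessment survey at 4 months". Section 12.1 analyses it by a repeated measures t-test, and section 2.0 describes a single cohort with no comparison group.

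**Baseline (7.1.4).** The Knowledge Assessment Survey is in the first list of assessments. The section then continues: "Following completion of the above baseline assessments, participants will be enrolled in the HALT-AD online program". Login instructions come after that.

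**Month 4 (7.1.5).** For a list that ends with the Knowledge Assessment Survey, "participants will complete the following assessments remotely via the REDcap survey tool". For the self-efficacy scale, the lifestyle risk assessment and the review of goals, the same section says: "Participants will also complete the following end of study assessments directly within the online HALT-AD program".

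**Course access (7.2.3).** Participants use the program "from home, with their own devices and at their own time". A resource library is provided, and "Participants will also be able to revisit course material as often as they would like".

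**Instruction to participants (Appendix 2, 16.1.1 Knowledge Assessment Survey).** The only direction on how to answer the 20 items is "Please read each statement carefully and choose whether you think the statement is True or False".

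**The concern.** A pre-post difference can be read as learning only if the test is taken under like conditions both times. Here one condition changes. The content the items relate to is out of reach at the first test and may be within reach at the second. Section 9.2.1 says the survey is to be developed as the program content is finalized, so the courses are a natural place to find answers.

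A participant who checked a course page at Month 4 would break no rule, because the protocol permits revisiting and never asks for unaided recall. Any such look-up adds to the change score. With one arm and a paired test, it cannot be told apart from learning. Section 1.2 says the pilot results will inform the second prototype, so a gain that mixes the two could make the courses look more effective than they are.

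**Working it through.** The plan states no expected change, standard deviation or power for this outcome (12.2), so there is no figure to reproduce. The check is first a comparison of conditions, then an illustration.

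**Conditions side by side**

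| Condition | Baseline | Month 4 |
|---|---|---|
| Mode | Remote, REDCap (7.1.1) | Remote, REDCap (7.1.1, 7.1.5) |
| General web search possible | Yes; internet access is required for inclusion (6.1) | Yes |
| Platform account | Not yet issued (7.1.4) | In use for other assessments (7.1.5) |
| Course pages | Not available | Not stated to be closed (7.2.3, 7.1.5) |
| Request to answer from memory | None (16.1.1) | None (16.1.1) |

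Only the account and course-page rows differ. Sections 7.1.4, 7.1.5, 9.2.1, 12.1 and 16.1.1 contain no time limit, supervision, pause in access or sensitivity analysis that would deal with them.

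**How many items the courses could answer.** By topic, items 1–5 are general, 6–10 loneliness, 11–15 sleep and 16–20 physical activity. Section 1.2 makes the loneliness course optional, and 7.2.1 offers sleep or physical activity. Matching by topic, the courses cover 5 + 5 = 10 items without the loneliness course and 5 + 5 + 5 = 15 with it.

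**Illustration.** Every input here except the 20 items and n = 20 is assumed. Suppose there is no true learning and unknown items are guessed with a 50% chance of success. For a baseline mean B, the number of unknown items is U = 2 × (20 − B). If a share f of these is looked up at Month 4 and none at baseline, the mean change is f × U × 0.5.

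| B | U | f | Mean change | Rejection, SD of change 2 | Rejection, SD of change 3 |
|---|---|---|---|---|---|
| 18 | 4 | 10% | 0.2 | 7% | 6% |
| 18 | 4 | 25% | 0.5 | 19% | 11% |
| 16 | 8 | 10% | 0.4 | 14% | 9% |
| 16 | 8 | 25% | 1.0 | 57% | 29% |
| 14 | 12 | 25% | 1.5 | 89% | 57% |

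Rejection is the chance that a paired t-test with n = 20 and two-sided 0.05 is significant (noncentral t). The level is assumed, since 12.1 states none. A mean change of 0.47 SD is the smallest that reaches significance.

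Two adjustments lower these figures:
- **Coverage.** If the courses answer only 10 of 20 items and the unknown items are spread evenly, the B = 16, f = 25% case becomes 0.25 × (8 × 10/20) × 0.5 = 0.5 points. With 15 of 20 it is 0.25 × (8 × 15/20) × 0.5 = 0.75.
- **Look-up at baseline.** If a share f₀ is searched on the web at baseline, the net change is (f − f₀) × U × 0.5. With f = 25%, f₀ = 10% and U = 8, this is 0.15 × 8 × 0.5 = 0.6 points. It is zero if the two shares are equal.

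**The case against.** A reader might infer that the test is closed-book at baseline and open-book at Month 4, or supervised at one time and not at the other. The documents do not support either. Both surveys are remote on REDCap under the same instruction, and many items are general health facts that can be searched at any time. Web look-up at baseline would reduce the measured change.

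A reader might also infer that the protocol leaves the courses open during the Month 4 survey. It does not say so. The sentence on revisiting belongs to a paragraph about three months of participation, and the survey follows completion of the program. Section 7.1.5 shows that accounts still work for questionnaires and goals; it is silent on course pages. Nor does any passage state that the survey is unsupervised. Appendix 1 groups it under procedures done on Zoom or REDCap, although 7.1.5 names REDCap.

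There are also reasons to expect little look-up. The instruction asks what the participant thinks, no pass mark is described for the survey, the payment in 7.5 does not depend on performance, several items have near-obvious answers, and some may have no matching course.

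All of this stands, and it narrows the point and rules out any firm statement of size. It does not remove the remaining difference: as far as the protocol states, course content is an additional source at Month 4 only, and nothing asks participants not to use it.

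**Conclusion.** The point holds in a limited form. The change in knowledge may include some answers looked up in course material at Month 4, and that component is upward because nothing at baseline matches it. General web look-up could act at either time, and its net effect has no known sign.

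The size cannot be estimated from the documents. The illustrated 0.2 to 1.5 points rests on assumed baseline means, look-up shares and standard deviations, on no true learning and on no look-up at baseline. It shows only that modest look-up could matter to a paired test of 20 people. The conclusion also assumes that course pages remain reachable when the survey is taken, which the protocol implies but does not state.

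It would go too far to say that the knowledge result is invalid. It is a secondary outcome labelled preliminary evidence in a pilot that was not powered for effect (12.2), and an uncontrolled change could not support a firm effectiveness claim in any case. The primary engagement outcomes in 4.1 are untouched. Severity: minor, worth fixing because the remedy is nearly free and the problem cannot be repaired once the data are in.

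**What to change.** 1. In Appendix 2, 16.1.1 Knowledge Assessment Survey, add one line to the instruction, in both languages and at both time points, for example: *Please answer from memory, in one sitting, without consulting the HALT-AD courses or any other material.* Using it at baseline as well keeps the two administrations alike and discourages web search at both.
2. In 7.1.5, make this survey the first Month 4 task, before the in-platform assessments. It is now last in the REDCap list, after surveys that ask participants to think back over the courses.
3. Optionally, use platform activity records to flag course access while the survey is open, and report the knowledge change with and without flagged participants. The fields listed in 7.4 are totals and averages, so the team must first confirm that time-stamped access is recorded.

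No lock on course access is needed. It would conflict with the free revisiting in 7.2.3, would have to spare the in-platform assessments, and would not stop web searches.

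The cost is one added line, a reordered task list and possibly a slightly smaller reported gain. The request relies on participants following it, so the report should still name possible look-up as a limitation.
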